14.7. Efficacy Assessment

The objective of these analyses is to explore the effects of XmAb18087 when administered repeatedly as a single agent across a range of dose levels, in combination with pembrolizumab, and at RD for each Part of the study.

The assessment of antitumor effects of XmAb18087 will be based on response criteria defined in RECIST 1.1 (Appendix A).

The number and percentage of subjects achieving a best overall response of complete response (CR; confirmed and unconfirmed), partial response (PR; confirmed and unconfirmed), stable disease, progressive disease, and not evaluable will be presented.

Overall response rate is defined as subject's best response of PR or better. The number and percent of subjects who achieved ORR will be summarized. Two-sided exact 95% confidence intervals for the ORR will be determined using the binomial distribution. The duration of objective response will be calculated from the time of initial response (PR or better) to the first documentation of relapse (recurrence after CR) or progression (after PR).

The evaluable population defined in Section 14.4 will be used for summary of ORRs and duration of response.

Depending on the completeness of the available follow-up data, an analysis of PFS, measured relative to Day 1, will be performed based on the Kaplan-Meier method. Median time and its 95% confidence interval, as well as the 25th and 75th quartiles with their 95% confidence intervals, will be summarized. Progression will be determined using the criteria described in RECIST 1.1 (Appendix A). The date of progression is defined as the date of progression or death.

Version 1.0 Page 103 of 145

The date of censoring for subjects who end the study without documented progression will correspond to the date the last tumor assessment was performed. Subjects who terminated from study without postbaseline tumor assessment will be censored at Day 1.

Progression-free survival will be presented based on the safety population for the overall study.

The potential antitumor effects of XmAb18087 may also be evaluated in other subgroups of subjects. The specifications for these and other similar analyses will be described in the SAP and supersedes any protocol specifications.

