7.7. Safety Run-in Cohorts

In each safety run-in cohort, no more than 1 subject will be initiated on treatment with XmAb18087 on any given day.

The planned initial XmAb18087 dose for all cohorts is $0.3 \,\mu\text{g/kg}$. Subsequent doses will then be escalated in steps (except for Cohort 1B, which will use $0.3 \,\mu\text{g/kg}$ for all doses) as indicated in Table 2, Table 3, and Table 4 in an effort to reduce the incidence and severity of CRS.

For all safety run-in cohorts in Part A, Part B, and Part C, the SRC will decide whether to advance to the next higher dose level cohort based on review of all available safety data. For each cohort, 3 subjects will be initially enrolled. If no subject experiences an adverse event of specific concern (AESC, as defined in Section 7.8 below), the SRC will be convened after all 3 subjects have completed one treatment cycle or discontinued treatment, whichever comes first. If 1 of the initial 3 subjects experiences an AESC, 3 additional subjects will be enrolled in that cohort (up to a total of 6 subjects) prior to convening the SRC. If 2 subjects experience an AESC, no additional subjects will be enrolled until the SRC has convened and made a recommendation based on the available safety data. Based on the type and severity of toxicities observed, the SRC may modify the safety run-in scheme (eg, decreases in dose level, smaller escalation steps, or other changes in the regimen), as long as the changes do not significantly affect the risk profile of the study.

If a subject discontinues treatment prior to completion of the first cycle due to an AE, that subject will not be replaced. If a subject discontinues treatment prior to completion of the first cycle for any other reason, an additional subject may be enrolled as a replacement.

Part A will begin by enrolling 3 to 6 subjects in Cohort 1A. After Cohort 1A dosing is demonstrated to be tolerable and is approved by the SRC, Part B will begin by enrolling Cohort 1B, which is one dose level lower than Cohort 1A.

Part C may begin concurrently with Part A.

The safety run-in portion will continue until establishment of an RD for expansion or until the repeated dose level reaches the highest dose planned in this study.

Enrolling additional subjects beyond 142 will require a protocol amendment.

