7.8.1. Replacement of Subjects

A subject enrolled in a safety run-in cohort who withdraws from study before completing the first cycle for reasons other than an AE will be considered to have inadequate data for evaluation by the SRC. In such cases, a replacement subject may be enrolled to receive the same dose of XmAb18087 (and pembrolizumab, when applicable) as the subject who withdrew prematurely. Subjects enrolled in the safety run-in cohorts who are discontinued from the study for any reason after the first cycle will not be replaced.

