14. STATISTICAL EVALUATION

14.1. Sample Size and Power

This study is being performed in 3 parts: MCC monotherapy (Part A), MCC combination therapy (Part B), and SCLC monotherapy (Part C). No formal power analyses were performed for efficacy endpoints for the initial dose escalation cohorts. After identification of each RD, Part A, Part B, and Part C will enroll expansion cohorts using a 2-stage design (Schultz, 1973).

In Part A, up to 9 subjects will be enrolled at the RD. If at least 1 subject shows a response by RECIST 1.1 criteria, then enrollment will continue up to a total of 22 subjects. A true response rate of 40% has statistical power of 84% to rule out a lower inactivity rate of 16% with a one-sided Type I error rate of 5%.

In Part B, up to 12 subjects will be enrolled at the RD. If at least 4 subjects show a response by RECIST 1.1 criteria, enrollment will continue up to a total of 30 subjects. A true response rate of 67% has statistical power of 84% to rule out a lower inactivity rate of 43% with a one-sided Type I error rate of 5%.

In Part C, up to 9 subjects will be enrolled at the RD. If at least 1 subject shows a response by RECIST 1.1 criteria, then enrollment will continue up to a total of 30 subjects.

Subjects who are not evaluable may be replaced. Up to 142 subjects will be enrolled. The total number of subjects enrolled will depend upon the number of safety run-in cohorts required to identify the RD for each Part. A true response rate of 30% has statistical power of 82% to rule out a lower inactivity rate of 11% with a one-sided Type I error rate of 5%.

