14.2. Statistical Methods

Before database lock, a statistical analysis plan (SAP) will be issued as a separate document, providing detailed methods for the analyses outlined below. Any deviations from the planned analyses will be described and justified in the final integrated clinical study report.

Unless otherwise specified, continuous variables will be summarized with N (ie, sample size), mean, median, standard deviation, minimum and maximum, and discrete variables will be summarized with frequencies and percentages. Safety and efficacy summaries will be performed for Parts A, B, and C separately and, for safety, also for the combined arms. For each Part, summary tables will be provided for each dose cohort and for the dose cohorts combined.

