14.4. Analysis Populations

The populations defined below will be used for analysis:

- **Safety population**: All subjects who are enrolled and receive at least 1 infusion of XmAb18087.
- Evaluable population: All subjects who are enrolled, receive at least 1 cycle (Parts A and C: 6 doses XmAb18087, Part B: 5 doses XmAb18087 and 1 dose pembrolizumab) of XmAb18087 and have at least 1 postbaseline RECIST 1.1 assessment of tumor imaging available.
- **PD population**: All subjects who are enrolled, receive at least 1 dose of XmAb18087 (and 1 infusion of pembrolizumab, when relevant for a particular PD assessment), and have at least 1 preinfusion and 1 postinfusion set of biomarker data available for analysis.
- **PK populations**: All subjects who are enrolled and receive at least 1 dose of XmAb18087 (ie, the XmAb18087 PK population) or 1 infusion of pembrolizumab (ie, the pembrolizumab PK population), and have at least 1 set of postinfusion PK data available for analysis.

Continuous data will be presented using descriptive statistics: number of subjects (N), mean, standard deviation, median, minimum, and maximum. Categorical data will be summarized by the number and percentage, where the percentage is presented in brackets to 1 decimal place. Safety and efficacy summaries will be provided for the monotherapy and combination therapy arms separately, as well as for the combined arms.

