19. PUBLICATION POLICY

By signing the clinical study protocol, the Investigator agrees with the use of results of the clinical study for the purposes of national and international registration, publication, and information for medical and pharmaceutical professionals. If necessary, the competent authorities will be notified of the Investigator's name, address, qualifications, and extent of involvement.

An Investigator shall not publish any data (poster, abstract, paper, etc.) without receiving approval from the Sponsor in advance. Authorship criteria for all publications of Xencor-sponsored clinical trials are based on the International Committee of Medical Journal Editors guidelines, "Uniform Requirements for Manuscripts Submitted to Biomedical Journals" (Uniform Requirements for Manuscripts Submitted to Biomedical Journals, 2010). Authorship credit can be granted only to those who make substantial contributions to the publication.

At a minimum, study results will be published on www.clinicaltrials.gov on all primary and secondary outcomes, no later than 1 year after completion of the study (including completion of the study if it has been terminated early).

This protocol and other study documents contain trade secrets and commercial information that is privileged and confidential. Such information is not to be disclosed unless required by laws or regulations. The PI agrees to use this information only in conducting this study and is not allowed to use it for other purposes without written consent from the Sponsor. Results obtained from this study are the property of the Sponsor.

Version 1.0 Page 111 of 145

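### Does restricting the primary ORR to an evaluable population bias a result that this terminated study will report?

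*Protocol*

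**What the plan says.** ORR, CR rate and PR rate are primary endpoints in every Part (Protocol 14.3.1). Protocol 14.7 assigns the population: "The evaluable population defined in Section 14.4 will be used for summary of ORRs and duration of response". Protocol 14.4 admits a subject only if they "receive at least 1 cycle (Parts A and C: 6 doses XmAb18087, Part B: 5 doses XmAb18087 and 1 dose pembrolizumab) of XmAb18087"; one or more RECIST assessments after baseline are required too. SAP 7 repeats that definition. PFS, in the same Protocol 14.7, uses the safety population.

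On replacement, Protocol 14.1 says "Subjects who are not evaluable may be replaced" and gives no limit by reason; SAP 6.1 repeats this. The run-in rules are tighter. Protocol 7.7 says "If a subject discontinues treatment prior to completion of the first cycle due to an AE, that subject will not be replaced", and Protocol 7.8.1 says run-in subjects "discontinued from the study for any reason after the first cycle will not be replaced".

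On reporting, Protocol 14.2 planned tables: "For each Part, summary tables will be provided for each dose cohort and for the dose cohorts combined". SAP 5.1, which records changes from the protocol, replaces this. It states that the study ended early with 4 enrolled subjects (2 in Part A, 2 in Part C), that efficacy analyses are dropped and that only listings will be produced. SAP 2 and SAP 10 say the same about listings. Protocol 19 promises that "study results will be published on www.clinicaltrials.gov on all primary and secondary outcomes", with the deadline running from study completion, "including completion of the study if it has been terminated early".

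**The concern.** Both entry conditions depend on what happens after treatment starts. A subject who dies, progresses or stops for toxicity before the last dose of the cycle is a treatment failure, yet leaves the denominator. An end-of-treatment scan showing progression (Protocol 7.9.3.3) does not bring the subject back, because the dose condition still fails. No all-treated ORR and no non-responder rule is given anywhere. If such subjects are also replaced, the expansion cohort fills up with people who got through the first cycle, while the result is compared with fixed inactivity rates. An inactive regimen could then pass more often than the stated 5%.

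Early termination does not obviously settle it. Protocol 19 still promises primary-outcome results, and the SAP sets no other denominator. With two subjects in a Part, one responder and one early failure is 1 of 2 or 1 of 1, depending on the population.

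**Working it through.** **1. The design figures.** Inputs from Protocol 14.1: Part A continues on at least 1 response in 9, total 22, rates 16% and 40%; Part B at least 4 in 12, total 30, rates 43% and 67%; Part C at least 1 in 9, total 30, rates 11% and 30%; one-sided 5%. The final cut-offs are not stated. I took the smallest total r that keeps the Type I error at or below 5%.

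P(success | p) = sum over x from the stage 1 minimum to n1 of P(X1 = x) × P(X2 ≥ r − x), where X1 ~ Bin(n1, p) and X2 ~ Bin(N − n1, p).

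| Part | r/N | Type I error | Power | Stated power |
|---|---|---|---|---|
| A | 7/22 | 4.97% | 83.9% | 84% |
| B | 18/30 | 4.55% | 84.3% | 84% |
| C | 7/30 | 3.88% | 82.2% | 82% |

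The stated power is reproduced.

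**2. What exclusion and replacement could do.** Let d be the share of treated subjects who never become evaluable. The documents give no value, so d is an assumption. Suppose none of them responds, all are replaced, and the inactivity rate p0 refers to all treated subjects. The response rate in the evaluable set is then p0/(1 − d). At d = 10%: 0.16/0.9 = 17.8%, 0.43/0.9 = 47.8%, 0.11/0.9 = 12.2%. Putting these into the same sum:

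| Part | d = 0 | d = 5% | d = 10% |
|---|---|---|---|
| A | 5.0% | 6.3% | 8.0% |
| B | 4.6% | 7.5% | 12.3% |
| C | 3.9% | 4.9% | 6.3% |

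**3. How far that depends on the assumptions.**
- No replacement: if the excluded subjects would not have responded, the number of responders is unchanged. The count rule keeps its design error of 5.0/4.6/3.9%.
- At most two replacements per Part, d = 10%: about 6.9/8.3/5.1% (simulation, 400,000 runs).
- Excluded subjects respond at half the evaluable rate q: p0 = q(1 − d) + qd/2 = q(1 − d/2). At d = 10%, q = p0/0.95, which is the d = 5% column.
- 16/43/11% are already evaluable-set rates: no excess.
- Enrolment cap: the run-in cohorts take 3 × 6 + 4 × 6 + 3 × 6 = 60 at most and the expansions 22 + 30 + 30 = 82, which makes the full 142. That leaves no replacement places. With 3 per run-in cohort, 142 − (30 + 82) = 30 remain. Full replacement at d = 10% needs 82/0.9 − 82 = 9.1.

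**4. The price of an all-treated analysis.** If 40/67/30% are evaluable-set rates, the all-treated rates at d = 10% are 36/60.3/27%. Power with the same cut-offs then falls to 73/59/72%.

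**5. The study as it ended.** Each open Part has two enrolled subjects. Protocol 7.7 starts every run-in cohort with three, so neither Part filled even its first cohort and no expansion or stage decision took place. Protocol 7.9.2 defines enrolment as confirmed eligibility, before dosing, so the documents do not say how many were treated. If both subjects in a Part were treated, exact 95% intervals are:

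| Case | All treated | Evaluable |
|---|---|---|
| 1 responder, 1 early failure | 1/2 = 50% (1.3–98.7%) | 1/1 = 100% (2.5–100%) |
| 0 responders, 1 early failure | 0/2 = 0% (0–84.2%) | 0/1 = 0% (0–97.5%) |

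If both completed the cycle and were scanned, the columns agree. Neither denominator supports a conclusion about activity.

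**6. What the listings show.** SAP 8.1 lists analysis population, dosing dates and reasons for ending treatment and study. SAP 10 lists the tumour-based efficacy data, and SAP 11.2 lists deaths. With four subjects, a reader can see every early failure and form either denominator.

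**The case for a change.** The strongest case for acting is that Protocol 19 is a firm commitment covering early termination, that the SAP does not reconcile it with dropping the efficacy analyses, and that anyone posting an ORR would turn to Protocol 14.7. One added SAP sentence would cost nothing and need no new data.

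Part of this stands. The two documents are not reconciled, and if response results are posted, the sensible form is counts by Part over all subjects who received at least one infusion, with those lacking a post-baseline assessment counted as non-responders and evaluable status shown. But Protocol 19 requires results, not a percentage on a given denominator, so an analyst can do this without an amendment. Harm would need a posted rate, a responder and an early failure in the same Part; the documents give no outcomes.

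The exclusion is also narrower than it first looks. A subject who receives every dose of the cycle and shows progression at the Day 40 scan stays in as a non-responder. Read strictly, the definition also drops a responder who missed a dose, which lowers the rate. The best-response table in Protocol 14.7 has a not-evaluable category and names no population, though such subjects can also arise within the evaluable set. Early deaths still count as PFS events (SAP Table 1).

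**Conclusion.** No change to the plan. The criticism is sound as a point of design: a denominator conditioned on completing a cycle, combined with open-ended replacement, could raise the Type I error to 8.0/12.3/6.3% in Parts A/B/C. That size rests on an assumed 10% loss, no responses among those lost, full replacement, inferred cut-offs, and inactivity rates that refer to all treated subjects. Without replacement, or with evaluable-set benchmarks, there is no excess.

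None of it reaches a result of this study. The SAP has withdrawn the ORR summary, no expansion cohort opened, and the listings show each subject's status. Rewriting the denominator for a possible later use of the design would concern a different trial. It could also lower power to 73/59/72% if the target rates are evaluable-set rates, so it is a trade-off and not a plain correction. What is left is how to present four subjects if results are posted, which an analyst can settle sensibly at that point.

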14.8. Pharmacokinetic Analysis

Pharmacokinetic parameters including C_{max} , t_{max} , $t_{1/2}$, $AUC_{0-\infty}$, CL, Vd, and Vd_{ss} will be estimated using either noncompartmental or compartmental methods, whichever best describes the observed data. Pharmacokinetic parameters for XmAb18087 will be compared with and without pembrolizumab administration.

Pharmacokinetic parameters at presumed steady-state will include area under the serum concentration-time curve during a dosing interval (t; AUC_t ; where t is 1 week), steady-state concentration (C_{ss}), minimum steady-state concentration ($C_{min,ss}$), steady-state fluctuation in concentrations (%Fluct), time of minimum concentration (t_{min}) and predicted accumulation (accumulation index, AI). The observed accumulation will be computed as the ratio of C_{max} and AUC_t at presumed steady state versus C_{max} and AUC_t after the first dose. Trough concentrations (C_{trough}) at predose will be used to evaluate the approach to steady state.

All PK parameters will be computed using actual elapsed time to PK sampling event and to dose event start and stop, calculated relative to the first dose start of infusion and the dose start for each infusion. Dose used to compute PK parameters will be the actual dose delivered during the infusion duration.

Dose proportionality across dose levels will be characterized by plotting C_{max} and $AUC_{0-\infty}$ and AUC_{t} versus dose. Similarly, the kinetic parameters $t_{1/2}$, t_{max} , CL, Vd, and Vd_{ss} across dose levels will be characterized by plots of these parameters versus dose.

Exploratory analyses may be performed to evaluate the relationship between 1 or more of the estimated PK parameters and selected safety, efficacy, and other serum protein assessment parameters described previously. The serum profile of XmAb18087 versus time will be evaluated with respect to any antibodies to XmAb18087 that may accelerate clearance.

A similar analysis of Pembrolizumab PK will be performed and details of both analyses will be described in a PK Analysis Plan.

14.9. Immunogenicity Assays

The incidence and titer of anti-XmAb18087 ADA will be reported by dose cohort and sample collection time point.

Version 1.0 Page 104 of 145

15. DIRECT ACCESS TO SOURCE DATA/NOTES

The Investigator or institution shall provide direct access to source data and documents for study-related monitoring, audits, IRB/Independent Ethics Committee (IEC) review, and regulatory inspection.

CONFIDENTIAL

The Sponsor or its designee will monitor the study according to GCP guidelines. The PI and study center will permit the Sponsor, its representatives, FDA, and other regulatory agencies direct access to all original source data and documents for study monitoring audits and inspections. All requested information must be entered into the eCRF in the EDC database. The completed eCRF must be promptly reviewed and electronically signed and dated by the PI.

The PI may be subjected to a field audit by the Sponsor, ICON, and/or FDA inspectors in order to validate the participation of subjects in the study and to verify the data reported in the clinical database. The Sponsor should be notified immediately of any audits scheduled by any regulatory authorities. Copies of audit reports from regulatory authorities should be promptly forwarded to the Sponsor.

The Sponsor and PI uphold the principle of the subject's right to protection against invasion of privacy. Throughout this study, all data collected and analyzed by the Sponsor will be identified only by an identification number.

ICON will provide the study sites access to the EDC database that will be used to collect the required subject eCRF data for this trial. The eCRF must be supported by the corresponding information in the source document.

Version 1.0 Page 105 of 145

16. QUALITY CONTROL AND QUALITY ASSURANCE

16.1. Conduct of the Study

To ensure compliance with GCP and all applicable regulatory requirements, the Sponsor or its representatives may conduct a quality assurance audit.

The study shall be performed in a manner that will implement and maintain quality control and quality assurance procedures with written SOPs to ensure that the study is conducted and data are generated, documented, and reported in compliance with the protocol, International Council for Harmonisation of Technical Requirements for Pharmaceuticals for Human Use (ICH) GCP, and applicable regulatory requirements.

The study will be conducted in compliance with the following:

- The protocol
- Ethical principles of the Declaration of Helsinki (Version 2013) and its amendments
- The principles of the GCP provided in the ICH Harmonized Tripartite Guidelines for GCP 1996
- FDA regulations (Code of Federal Regulations [CFR], Sections 312.50 and 312.56)
- All applicable national laws and regulations including but not limited to country-specific GCP

Any significant protocol deviations must be documented on the eCRF.

